National Co-Principal Investigator Heart Failure Cardiologist	[name] Chief, Division of Cardiovascular Medicine Ohio State University [contact]
Manufacturer	Sunshine Heart, Inc. [name] Tele: [name] [contact] www.sunshineheart.com

Clinical/Technical Support [contact]-SHPULSE)

INTRODUCTION

PURPOSE

Sunshine Heart Inc. is sponsoring a prospective, multi-center trial to assess the safety and provide indications for performance of the Sunshine Heart C-Pulse® System (“C-Pulse®”).

The purpose of the study is to determine whether use of C-Pulse® as treatment for patients in moderate to severe heart failure (HF) is associated with reasonable assurance of safety and performance, such that the C-Pulse® merits Food and Drug Administration (FDA) approval for continuation into a pivotal study to examine the safety and efficacy of C-Pulse® for US market approval.

STUDY SIZE AND DURATION

This clinical study is expected to commence September 2008. The duration of the study is expected to be 120 months. The primary study population will include 20 patients enrolled and implanted with C-Pulse® in up to 7 centers in the United States (US) and potentially some Outside the United States (OUS) centers. This expansion protocol will allow 40 patients to be enrolled and implanted in up to 9 centers. The first 40 patients that meet all eligibility criteria will proceed to implantation. Up to approximately 60 patients will be enrolled and consented for performing screening and testing required to confirm eligibility, such as Computed Tomography (CT) scan. All patients must be consented prior to performing any study related procedures. A patient is considered enrolled upon signing the informed consent. To minimize the burden to the patient, data collected as standard of care and not for the specific reason for study eligibility may be used for baseline data points as outlined in the informed consent. These tests will suffice for the baseline dataset if collected within the screening timeframe of 30 days prior to implant.

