Device malfunction denotes a failure of one or more of the components of the MCSD system which either directly causes or could potentially induce a state of inadequate circulatory support (low cardiac output state) or death. The manufacturer must confirm device failure. A failure that was iatrogenic or recipient-induced will be classified as an Iatrogenic/Recipient-Induced Failure.

Device failure should be classified according to which components fails as follows:

- 1) **Pump** failure (implanted components of pump and any motor or other pump actuating mechanism that is housed with the implanted components). In the special situation of **pump thrombosis**, thrombus is documented to be present within the device or its conduits that result in or could potentially induce circulatory failure.

- 2) **Non-pump** failure (e.g., external pneumatic drive unit, electric power supply unit, batteries, controller, interconnect cable, compliance chamber).

Hemolysis

A plasma-free hemoglobin value that is greater than 40 mg/dl, in association with clinical signs associated with hemolysis (e.g., anemia, low hematocrit, hyperbilirubinemia) occurring after the first 72 hours post-implant. Hemolysis related to documented non-device-related causes (e.g. transfusion or drug) is excluded from this definition.

Hepatic Dysfunction

An increase in any two of the following hepatic laboratory values (total bilirubin, aspartate aminotransferase/AST and alanine aminotransferease/ALT) to a level greater than three times the upper limit of normal for the hospital, beyond 14 days post-implant (or if hepatic dysfunction is the primary cause of death).

Hypertension

New onset blood pressure elevation greater than or equal to 140 mm Hg systolic or 90 mm Hg diastolic (pulsatile pump) or 110 mm Hg mean pressure (rotary pump).

Major Infection

A clinical infection accompanied by pain, fever, drainage and/or leukocytosis that is treated by anti-microbial agents (non-prophylactic). A positive culture from the infected site or organ should be present unless strong clinical evidence indicates the need for treatment despite negative cultures. The general categories of infection are listed below:

Localized Non-Device Infection

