The secondary objectives are descriptive in nature and will be evaluated in order to gain additional information regarding the C-Pulse® system. There are no specified performance criteria for these objectives. For continuous measures the mean, standard deviation, minimum and maximum values will be presented. For categorical variables the frequency and percent will be presented.

Endpoints consistent with the primary safety and efficacy objectives will be evaluated at all additional time points.

1. The adverse event rate will be presented at 3, 6, 12 and 18 months post-procedure, and annually for years 2-5 post-procedure.
2. The change from baseline to follow-up will be evaluated for peak VO₂, Six Minute Hall Walk, MLWHF, Fatigue Impact Scales and heart failure symptoms from NYHA.

The device failure rate will be quantified. Failure will be defined as both failure of the device, and failure of the device to be programmed to the treatment.

Additionally, the adverse event rate for each of the adverse events described in the Adverse Event Definitions section – pages 36-40 – will be provided. Exact 95% two-sided confidence intervals with an underlying Binomial Distribution will be provided for each event. Adverse events will also be tabulated by attribution (seriousness, device-relatedness, and procedure-relatedness) according to the CEC.

The following additional efficacy measures will be analyzed at each time point to evaluate the efficacy of the C-Pulse® System. For these measures the averages and the average change from baseline to each follow-up period will be presented along with the trend over time:

- Hemodynamic measures are from right heart catheterization (RHC): Cardiac Index (CI), Pulmonary Artery Pressure (PAP), Pulmonary Capillary Wedge Pressure (PCWP), and Cardiac Output (CO).
- Quality of Life
 - Kansas City Questionnaire.
- Blood tests (e.g. Serum sodium, serum creatinine, serum bilirubin, hemoglobin, ALT and AST).
- Concomitant cardiovascular medications

The following measures will also be summarized:

- Re-hospitalization (HF-related and all-cause)
- Duration of support/survival duration.
- Length of time to ICU and hospital discharge
- Device evaluation – Device log and C-Pulse® User log will be evaluated and summarized. Average daily device use will be provided for each time period.

Sample Size Determination

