The Cuff needs to comply to the natural shape of the ascending aorta to not cause local pressure. The wrap is designed to maintain the actuator in position on the aorta, and to ensure it deflects inward. A pre-shaped wrap made of woven Dacron, and with some strain relief feature in the top and bottom edges of the cuff to better transition from the cuffed aorta to the non-cuffed aorta has been used. Woven Dacron has proven long-term use clinically as both a peri-vascular wrap and as a graft replacement, and has only 5% stretch long-term *in vivo*. It is secured to itself using standard suturing.

The inflation fluid is filtered room air. Accelerated over-pressure device testing indicates that the balloon is very unlikely to fail within the first four years of continuous use. Premature failure may occur if the inflation membrane of the Cuff migrates under the wrap and causes a crease line and counterpulsation is continued. The expected consequences of a persistent leaking balloon may include surgical emphysema or pneumothorax. Leakage of non-sterile air may also predispose to mediastinal infection. There is negligible risk of air embolism if the aorta is not compromised.

There is a risk of a needle puncture hole being made intra-operatively. Surgeons are required to undergo multiple implantations of the cuff on a mock inflated ascending aorta prior to their first implantation, and there is an intra-operative check-list to reduce the chance of making an inadvertent needle-hole, and to check for and discover any such hole and thus replace the cuff.

The Driver is designed to detect air leaks and trigger an alarm and to stop. The Driver is designed to detect air leaks and will immediately alarm and stop if a major leak occurs.

The electronic system is also used to detect impending malfunctions by performing diagnostic tests on the system. Safety features built into the Driver are designed to protect the patient in the event of system failure, as well as to protect the integrity of the system. Safety features include protection against current leakage, defibrillating voltages, failure of the microprocessor and power supply and over-inflation of the Cuff.

Device stoppage for any reason is not immediately dangerous to the patient, but the symptoms of heart failure may return. The device is engineered to resume a deflated state if there is a power loss or malfunction, thus the natural blood pathways of the heart and vasculature are preserved.

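### Device Malfunction depends on a low-output test and on sponsor confirmation, and is not reconciled with the device failure rate, so failures that stop counterpulsation may be under-counted

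*Combined protocol and SAP*

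**What the plan says.** **Definition.** Adverse Event Definitions, Device Malfunction, covers a failure of one or more system components "which either directly causes or could potentially induce a state of inadequate circulatory support (low cardiac output state) or death". It adds: "The manufacturer must confirm device failure". A further sentence reads: "A failure that was iatrogenic or recipient-induced will be classified as an Iatrogenic/Recipient-Induced Failure". Failures are then split into pump and non-pump. The non-pump examples are "external pneumatic drive unit, electric power supply unit, batteries, controller, interconnect cable, compliance chamber". The opening of that section says the definitions follow a mechanical circulatory support registry, apart from Major Bleeding and an added Aortic Disruption event.

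**Device.** Background and Indications for Use describe an augmentation device that is neither obligatory nor life-supporting. Background calls the risk of death or disability in failure modes low, apart from returning symptoms. Risk Analysis, Device Failure, says: "Device stoppage for any reason is not immediately dangerous to the patient, but the symptoms of heart failure may return". It names surgical emphysema and pneumothorax as expected consequences of a persistently leaking balloon.

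**Analysis.** Device failure rate is a named secondary objective. Statistical Methods, Secondary Objectives, says it will be quantified and defines it in one sentence: "Failure will be defined as both failure of the device, and failure of the device to be programmed to the treatment". The next paragraph separately plans a rate with an exact two-sided 95% interval for each defined adverse event, which includes Device Malfunction.

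**The concern.** The definition tests for an outcome that suits a pump carrying the circulation. For this device, the protocol's own account of a typical failure is that counterpulsation stops and symptoms return, or that a leak causes a local complication. Such a failure can be genuine and still be judged not to meet the low-output or death condition. Confirmation is a second filter, held by the company whose device is under test. The plan gives no rule for devices that are not returned or whose analysis is inconclusive.

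The separate device failure rate could have closed the gap, but its definition leaves open what counts. At stake are a named secondary objective and the malfunction rate. Both inform the Data and Safety Monitoring Board's (DSMB) judgement of safety and the design of the pivotal study.

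**Working it through.** The plan states no expected malfunction rate, event count or power for this item, so there is no figure to reproduce. The check compares the texts and then illustrates size.

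**1. Who confirms.** The contact table names the company as manufacturer. The Purpose section says "Sunshine Heart Inc. is sponsoring a prospective, multi-center trial". Manufacturer and sponsor are the same company.

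**2. How far the definition was adapted.** Aortic Disruption was added and the internal infection event was rewritten around the Cuff. Device Malfunction still lists thrombosis within the pump, although System Features says clotting inside the mechanism is eliminated. It also lists a compliance chamber. The low-output clause comes from the same template.

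**3. The two rates side by side.**

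| Feature | Device Malfunction | Device failure rate |
|---|---|---|
| Where | Adverse Event Definitions | Statistical Methods, Secondary Objectives |
| Low-output or death condition | Yes, actual or potential | Not stated |
| Manufacturer confirmation | Required | Not stated whether it applies |
| What counts as failure | Component failure meeting the condition | Failure defined as failure (circular), plus failure to be programmed |
| Time base | 3, 6, 12, 18 months, years 2 to 5 | None stated |

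The malfunction definition uses malfunction and failure interchangeably, so a reader cannot tell whether its conditions carry over to the second rate.

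**4. Size.** Inputs: n = 40 implanted (Study Size and Duration; Design) and the exact binomial interval named in the plan. One patient is 1/40 = 2.5 points. Sample Size Determination still speaks of 20, where one patient would be 1/20 = 5 points, but the current plan is 40.

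Two quantities are assumptions: the true proportion of patients with a component failure (q, 10% to 30%) and the share judged to meet the low-output clause (f, 0 to 100%). The expected number counted is 40 × q × f:

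| q | f = 0 | f = 25% | f = 50% | f = 100% |
|---|---|---|---|---|
| 10% | 0 | 1 (2.5%) | 2 (5%) | 4 (10%) |
| 20% | 0 | 2 (5%) | 4 (10%) | 8 (20%) |
| 30% | 0 | 3 (7.5%) | 6 (15%) | 12 (30%) |

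The Clopper-Pearson limits are the 2.5% quantile of Beta(x, n − x + 1) and the 97.5% quantile of Beta(x + 1, n − x). For x = 0 the upper limit is 1 − 0.025^(1/40) = 8.8%. For the q = 20% row:

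- 0/40 = 0% (0 to 8.8)
- 2/40 = 5% (0.6 to 16.9)
- 4/40 = 10% (2.8 to 23.7)
- 8/40 = 20% (9.1 to 35.6)

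The same eight failing patients can thus be reported anywhere from 0% to 20%, depending on how the clause is read.

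**The case against.** Much can be said for the plan, and several stronger readings fail.

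- **Stoppage never causes low output or death.** A reader might infer that the protocol says this, so that no failure could qualify. It says only that stoppage is not immediately dangerous and that the risk is low. The clause extends to potential harm, and the driver and batteries are listed as failure classes. Exclusion is possible, not certain.
- **The primary safety composite is understated too.** The documents do not support this. Primary Safety Measures takes in any adverse event that the CEC adjudicates as device-related, without needing the malfunction label or sponsor confirmation. A pneumothorax or infection from a leak can enter that way. A stop with no clinically relevant health change may not be an adverse event at all, but that is a narrower matter.
- **Leads are excluded.** The non-pump list is given as examples and includes an interconnect cable. Implanted parts fall under pump failure. Omitting the leads by name excludes nothing.
- **Iatrogenic failures vanish.** Risk Analysis says "There is a risk of a needle puncture hole being made intra-operatively", so the class matters. The text only classifies such failures separately. It does not say whether they enter the rate.
- **The failure sentence needs a hardware and a programming fault together.** The ordinary reading is that it covers both kinds.
- **Failures go unrecorded.** Driver alarms and events are downloaded at follow-up, a system modification requires an adverse event form, and explanted parts are to be returned. The data largely exist. What is missing is a rule for counting them.

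Two points on the other side stand in full. These outputs are descriptive, with no performance criterion, in an unpowered feasibility study. Registry alignment also has value, because the protocol intends to weigh the serious adverse event profile against other circulatory support devices. That argues for adding a count and keeping the registry definition.

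**Conclusion.** The concern holds in limited form. The Device Malfunction definition is not adapted to a non-obligatory device and makes sponsor confirmation a condition. It is not reconciled with a device failure rate that is circularly defined and has no time base. Failures that stop counterpulsation but only bring back symptoms, or that the sponsor does not confirm, may be under-counted in the malfunction rate. They may also be under-counted in the failure rate if the same conditions are taken to apply.

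Each such patient is worth 2.5 points at 40 implanted. The contrast between 0% and 20% rests on an assumed eight failing patients, none judged to meet the clause. It shows sensitivity to wording and does not forecast the result. The change should be made, but the point does not undermine the primary safety analysis.

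**What to change.** In Statistical Methods, Secondary Objectives, replace the failure sentence with a definition that does not depend on clinical consequence:

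- Device failure is any failure of the Cuff, Percutaneous Interface Lead, sense lead, Driver or Battery Carrier to deliver counterpulsation as programmed, whatever the hemodynamic result.
- The CEC classifies each case. The manufacturer's engineering report is evidence, not a condition.
- Unconfirmed failures and unreturned devices are counted.
- Iatrogenic and recipient-induced failures are shown as a subset within the total.
- Results are given by component at the time points already listed for adverse events, with failures per device-year (failures divided by total device-years of support). The listed points stop at year 5 while visits run to year 10, so the per-device-year figure should use all follow-up.

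Keep the registry-defined Device Malfunction rate as a separate line, so that comparison with other devices is preserved.

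The cost is wording in the statistical section and the CEC charter, some added classification work for the existing committee, and a second line to report. Driver logs and forms are already collected. The reported failure rate is likely to be higher.
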